4 OBJECTIVES AND ENDPOINTS

The objective and endpoints for this study are shown in [Table 4-1](#).

Table 4-1: Objectives and Endpoints

Objectives	Endpoints
Primary	

 Part 1: Dose Escalation To determine the safety, tolerability, DLTs, and MTD/MAD/alternative dose of BMS-986242 administered as monotherapy (lead-in cycle) and in combination with nivolumab in participants with advanced malignant tumors Part 2: Dose-Expansion Cohort(s) To evaluate the safety and tolerability of BMS-986242 in combination with nivolumab in participants with advanced malignant tumors 	
 Incidence of DLTs, AEs, SAEs, AEs leading to discontinuation, deaths, and clinical laboratory test abnormalities Additional safety endpoints include changes from baseline in laboratory parameters, vital signs, and ECGs.
Secondary	

 To characterize the PK of BMS-986242 administered alone and in combination with nivolumab To characterize the pharmacodynamic activity of BMS-986242 administered alone and in combination with nivolumab To characterize the immunogenicity of nivolumab when administered in combination with BMS-986242 To assess the preliminary anti-tumor activity of BMS-986242 administered in combination with nivolumab in advanced malignant tumors 	
 Summary measures of selected BMS-986242 PK parameters, such as Cmax, Tmax, AUC(TAU), AUC(INF), Ctrough, T-HALF, CLT/F, Vss/F, AI, %UR24, %UR72, and exposure ratios of select BMS-986242 metabolites to BMS-986242 from concentration-time data during BMS-986242 monotherapy and BMS-986242 Ctrough during combination treatment Summary measures of change from baseline (and/or percent change) for serum and tumor kynurenine and related metabolites Incidence of ADA to nivolumab in combination with BMS-986242 ORR in participants with a BOR of CR or PR per RECIST version 1.1 for solid tumors; mDOR, and PFSR at 6, 9, 12, and 24 months

[REDACTED]
 
[REDACTED]
 
[REDACTED]
 
[REDACTED]
 
[REDACTED]
	
[REDACTED]
 
[REDACTED]
 
[REDACTED]
 
[REDACTED]
 
[REDACTED]

Table 4-1: Objectives and Endpoints

Objectives	Endpoints

[REDACTED]
	
[REDACTED]

Abbreviations: %UR24 = percent urinary recovery over 24 hours; %UR72 = percent urinary recovery over 72 hours

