7.4.2 Guidelines for Dose Modification

Participants will be monitored continuously for AEs while on study treatment. Participants will be instructed to notify their physician immediately for any and all AEs. The criteria presented in this section and [Table 7.4.2-1](#) for dose modifications for BMS-986242 and delays are meant as general guidelines.

Participants will continue to receive study treatment as long as they have not had disease progression or study treatment-related AEs requiring dose modification as described below.

- Dose modification, interruption, or delay may occur in the setting of a lower-grade AE and/or be more conservative than indicated in [Table 7.4.2-1](#) based on the clinical judgment of the investigator and in consultation with the Sponsor/Medical Monitor.
- Dose reductions of BMS-986242 should be to the previous lower dose level.
- If several AEs of varying grades or severities occur simultaneously, the dose modification applied should be the greatest reduction applicable.
- Assessment of causality (chronology, confounding factors such as disease, concomitant medications, diagnostic tests, and previous experience with the agent) must be determined and documented by the investigator prior to dose modification.
- If the same AE recurs despite a dose reduction, a second dose reduction versus discontinuation of BMS-986242 will be discussed and agreed upon by the Sponsor/Medical Monitor and investigators.
- No more than 2 dose reductions of BMS-986242 will be allowed per participant. If a third dose reduction is required, the participant must discontinue BMS-986242. Dose re-escalation after a dose reduction may occur in limited circumstances (such as a change in attribution of an AE) after discussion and agreement of the Sponsor/Medical Monitor and investigators.
- Skipped doses will not be administered within the same cycle.
- For an AE requiring dose modification, BMS-986242 and nivolumab should be interrupted to allow recovery from the AE. Re-initiation of study treatment cannot occur until AE decreases to \leq Grade 1 or baseline assessment. In case of delayed recovery to \leq Grade 1 or baseline (except for alopecia) from treatment-related AEs that results in a delay of treatment for $>$ 6 weeks, the participant will not receive additional protocol-related treatment and will be removed from study unless discussed and agreed upon by the Sponsor/Medical Monitor and

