investigators that it is in the best interest of the participant to receive additional treatment with BMS-986242 and nivolumab (eg, if the participant has demonstrated a response to treatment).

- During the DLT evaluation period, if a participant receives dose reduction and experiences a DLT at the lower dose, this DLT will be attributed to the highest dose level administered.
- For data collection and analysis purposes, all participants will continue to be classified by the original treatment arm.

Table 7.4.2-1: Dose Modifications

Dose Modification Criteria for Study Treatment-Related Adverse Events	BMS-986242 Monotherapy Modification at the Next Dose	BMS-986242 Combination Modification at the Next Dose
QTcF > 500 msec confirmed by at least 1 repeat ECG and at least 60 msec above baseline	Interrupt if needed to optimize electrolyte management. If event persists after electrolyte optimization (including dose modification of BMS-986242, if necessary), discontinue. Participants may proceed to get nivolumab monotherapy.	Interrupt if needed to optimize electrolyte management. If event persists after electrolyte optimization (including dose modification of BMS-986242, if necessary), discontinue. However, treatment with nivolumab may continue after discussion between PI and Medical Monitor.
Any other study treatment-related \geq Grade 3 adverse event that does not meet permanent discontinuation criteria (Section 8)	Decrease 1 level of BMS-986242 (no lower than 25 mg).	Decrease 1 level of BMS-986242 (no lower than 25 mg) in combination with same dose of nivolumab.
Grade 2 LFT abnormalities that do not resolve within 1 week	Interruption of BMS-986242 Continuation of BMS-986242 at a lower dose level may be considered after discussion with the Study Director/Medical Monitor. Participants may proceed to get nivolumab monotherapy.	NA
Grade 2 LFT abnormalities that resolve in 1 week	Interrupt dosing until improvement to Grade 1 or baseline and resume at same dose. If recurrence of Grade 2 LFT elevations, decrease 1 level.	NA

Abbreviations: LFT = liver function test; QTcF = QT interval corrected for heart rate using Fridericia’s formula; NA = not applicable; PI = principal investigator.

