9.5.2 Pharmacokinetic Assessment Following Combination Treatment with BMS-986242 and Nivolumab

Plasma samples for BMS-986242 will be collected for all participants receiving combination treatment with BMS-986242 and nivolumab. Plasma concentration data will be tabulated using summary statistics. These data, together with data from the monotherapy, may also be pooled with other datasets for PPK analysis, which will be presented in a separate report.

Serum samples for nivolumab PK and immunogenicity assessments will be collected for all participants receiving combination treatment of BMS-986242 and nivolumab. End-of-infusion and trough concentrations will be tabulated using summary statistics. These data may also be pooled with other datasets for PPK analysis, which will be presented in a separate report.

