10.2 Populations for Analyses

For purposes of analysis, the following populations are defined as follows:

Population	Description
Enrolled	All participants who sign informed consent and are registered into the IRT
Treated	All participants who received at least 1 dose of study treatment
Pharmacokinetic	All treated participants who have available concentration-time data from the participants who received any BMS-986242 or nivolumab
Immunogenicity	All treated participants who have received nivolumab and have a baseline and at least 1 post-treatment immunogenicity measurement
Biomarker	All treated participants who have available biomarker data

Note: Analyses of safety, extent of exposure, biomarkers, PK, efficacy, and pharmacodynamics will be based on the treated population.

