10.3.3 Other Analyses

Table 10.3.3-1: Pharmacokinetic Analyses for BMS-986242 and Nivolumab

Endpoint	Statistical Analysis Methods
BMS-986242	
C _{max} , AUC(TAU), AUC(0-T), AUC(INF), C _{trough} , CLT/F, V _{ss} /F, AI, %UR ₂₄ , %UR ₇₂ , MR_C _{max} , MR_AUC(TAU)	Summary statistics: geometric means and coefficients of variation
C _{max} , AUC(TAU), AUC(INF) (Only)	Scatter plots vs dose for each day measured; dose proportionality based on a power model and a CI around the power coefficient
T-HALF	Summary statistics: means and standard deviations
T _{max} .	Summary statistics: medians and ranges

Table 10.3.3-1: Pharmacokinetic Analyses for BMS-986242 and Nivolumab

Endpoint	Statistical Analysis Methods
Ctrough and Ceoi	Summary statistics to assess attainment of steady state: geometric means and coefficients of variation, by treatment and by day; plots vs time by dose
Nivolumab	
Ctrough and Ceoi	Summary statistics: geometric means and coefficients of variation, by treatment and by day, plots vs time by dose

Abbreviations: AI = accumulation index, calculated based on ratio of AUC and Cmax at steady state to after the first dose; AUC(0-T) = area under the concentration-time curve from time zero to the time of the last quantifiable concentration; AUC(TAU) = area under the concentration-time curve in one dosing interval; Ceoi = concentration at the end of infusion; CLT/F = apparent total body clearance; Cmax = maximum observed concentration; Ctrough = trough observed plasma concentration; Tmax = time of maximum observed concentration; Vss/F = apparent volume of distribution at steady-state.

Geometric means and geometric mean ratios for Cmax and AUC(0-T) will be estimated for participants in the substudy exploring food effect. PK time-concentration data may be pooled with data from other studies for PPK analysis, which will be presented in a separate report.

A concentration-response analysis may be used to characterize the effects of BMS-986242 on QTcF, based on data from the clinical pharmacology substudy QTc assessment. Additional ECG data and time matched concentrations may be pooled from other studies to perform an integrated analysis. The results of the analysis will be reported separately.

[REDACTED]	[REDACTED]

[REDACTED]

Table 10.3.3-3: Immunogenicity Analyses

Endpoint	Statistical Analysis Methods

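### Read as written, the original-arm rule places BMS-986242 troughs drawn after a dose reduction under the assigned dose, lowering later-visit Ctrough at 50 mg and above wherever reductions occur

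*Combined protocol and SAP*

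**What the plan says.** Section 7.4.2 ends its list of dose-modification rules with "For data collection and analysis purposes, all participants will continue to be classified by the original treatment arm". The bullet just before it deals with attributing a DLT after a reduction, but the rule itself is not limited to safety.

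The same section sets the size and number of reductions: "Dose reductions of BMS-986242 should be to the previous lower dose level", and "No more than 2 dose reductions of BMS-986242 will be allowed per participant". For other treatment-related events of Grade 3 or higher, Table 7.4.2-1 reads "Decrease 1 level of BMS-986242 (no lower than 25 mg", with the bracket closing there. The floor is not repeated in the Grade 2 liver-test rows. Re-escalation is possible in limited circumstances.

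On the pharmacokinetic side, Section 4 names "BMS-986242 Ctrough during combination treatment" among the secondary endpoints. Table 10.3.3-1 gives its analysis as "Summary statistics to assess attainment of steady state: geometric means and coefficients of variation, by treatment and by day; plots vs time by dose". Section 9.5.2 says of the combination period only that "Plasma concentration data will be tabulated using summary statistics". The pharmacokinetic population in Section 10.2 is "All treated participants who have available concentration-time data from the participants who received any BMS-986242 or nivolumab". Section 9.5.1 calls for actual sampling times but does not mention actual dose. Section 10.3 describes itself as a summary and leaves the full SAP to be finalised before database lock.

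**The concern.** Keeping a participant in the assigned group is a sensible convention for counting adverse events or responses. A concentration is different, because it reflects the dose taken before the sample. If a participant assigned 200 mg is cut to 100 mg and a trough is drawn later, the original-arm rule files that value under 200 mg.

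The stated purpose of the Ctrough summary is to see whether steady state has been reached, and that presupposes constant dosing. If reductions accumulate over visits, the pooled geometric mean drifts down and the CV goes up. The drift could be read as failure to hold steady state, as induction, or as an effect of nivolumab.

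Part 2 is the most exposed. It has no Cycle 0, so its Cycle 1 Day 1 predose sample precedes any BMS-986242. Its first on-treatment trough is at Cycle 3 Day 1, after 8 weeks of treatment, and there is no earlier trough at the assigned dose to compare it with.

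**Working it through.** The documents state no precision or sample-size figure for Ctrough, so there is nothing of the plan's own to reproduce first.

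**Inputs**
- Dose levels (Table 5.1.2.1-1): 12.5, 25, 50, 100, 200, 400 and 600 mg.
- One step down: r = 0.5 from 50, 100, 200 or 400 mg; r = 400/600 = 0.667 from 600 mg.
- Two steps down: r = 25/100 = 50/200 = 100/400 = 0.25; r = 200/600 = 0.333 from 600 mg. From 50 mg, the 25 mg floor in the Grade 3 row allows only one step. Under that row 12.5 and 25 mg are not reduced.
- Trough visits (Table 9.5.3-1): Cycle 0 (Part 1), Cycle 1 Day 1, Cycle 3 Day 1, every 4 cycles from Cycle 5 Day 1, and end of treatment.
- f, the share of samples at a visit drawn after a reduction: an assumption of 10% to 30%, because no reduction rate is given.
- Log-scale SD of 0.23: the value Section 10.1.1 uses for Cmax, taken from a related compound. It is borrowed for illustration because none is given for Ctrough.
- Troughs are assumed proportional to dose.

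**Step 1: geometric mean.** If the log mean at the assigned dose is m, samples drawn after a reduction have log mean m + ln r. The pooled log mean is m + f ln r, so the geometric mean is multiplied by r^f and the bias is r^f - 1. Example: 0.5^0.1 = 0.933, or -6.7%.

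| Reduction | r | f = 10% | f = 20% | f = 30% |
|---|---|---|---|---|
| One step from 50, 100, 200 or 400 mg | 0.5 | -6.7% | -12.9% | -18.8% |
| 600 to 400 mg | 0.667 | -4.0% | -7.8% | -11.5% |
| Two steps from 600 mg | 0.333 | -10.4% | -19.7% | -28.1% |
| Two steps from 100, 200 or 400 mg | 0.25 | -12.9% | -24.2% | -34.0% |

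The two-step rows treat every sample counted in f as twice-reduced. At f = 0 the bias is zero.

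**Step 2: CV.** If reduction is unrelated to exposure, the pooled log variance is SD² + f(1 - f)(ln r)². For one halving at f = 10%: 0.0529 + 0.09 × 0.4805 = 0.0961, so CV = √(e^0.0961 - 1) = 31.8%, against 23.3% with no reductions. At f = 20% and 30% it is 37.2% and 40.8%.

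**Step 3: which visits.** Summaries are by day. The Cycle 1 Day 1 predose trough is touched only by a reduction during Cycle 0. In Part 1, Cycle 3 Day 1 comes 2 + 4 + 4 = 10 weeks after the first dose, so the effect falls mainly there and later.

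**Step 4: what a remedy recovers.** Toxicity may track exposure. This was simulated with 1,000,000 participants, one halving and log SD 0.23, with high-exposure participants more likely to be reduced. Values are ratios to the true geometric mean at the dose named.

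| Handling | f = 10% | f = 20% | f = 30% |
|---|---|---|---|
| Original label | 0.933 | 0.871 | 0.812 |
| Post-reduction samples excluded | 0.963 | 0.935 | 0.909 |
| Reduced participants relative to the lower dose | 1.399 | 1.307 | 1.248 |

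Moving these samples into the lower dose would therefore contaminate that dose. Dose-normalising all samples returns the ratio to 1.00 if proportionality holds. With a log SD of 0.5 instead, exclusion gives 0.922, 0.864 and 0.813, about the same as the original label, so exclusion alone is not enough.

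**The case against.** The strongest reply is that the plan never states the faulty rule. Section 7.4.2 classifies participants and does not assign a dose to a sample. Table 10.3.3-1 uses both treatment and dose as groupings and says of neither whether it is assigned or actual. Section 10.3 leaves detail to an SAP not yet written. This stands as a limit on certainty: pooling under the assigned dose is the default reading, not an explicit pharmacokinetic rule. It does not dispose of the point, because the only classification rule now in the protocol covers all analyses and points the wrong way for concentrations.

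A summary by assigned dose is also a legitimate description of what participants assigned that dose attained, if labelled so. That is fair, but it does not serve the stated aim of judging steady state.

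Many severe events lead to permanent discontinuation under Section 7.4.5, which removes troughs and does not lower them. That may keep f small.

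Three stronger readings are tempting, and the documents do not support them.
- A reader might infer that the dose-proportionality analysis is distorted. The power model covers Cmax, AUC(TAU) and AUC(INF), not Ctrough, and rests mainly on Cycle 0 and substudy data. Day 1 cannot be affected. Day 14 is affected only if an event, recovery and restart at a lower dose all fall within two weeks.
- A reader might infer that escalation decisions are corrupted. They rest on a 6-week window that closes before Cycle 3 Day 1.
- A reader might extend the point to pharmacodynamic summaries. Part of Section 10.3.3 is redacted, so their handling cannot be judged.

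**Conclusion.** The point holds in limited form. Followed as written, the protocol files post-reduction troughs under the assigned dose. This lowers geometric mean Ctrough and inflates its CV at levels of 50 mg and above, mainly from Cycle 3 Day 1. The 12.5 and 25 mg levels are essentially unaffected.

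The direction follows from the text wherever reductions occur, given that a lower dose yields a lower trough. The size does not: it rests on proportional kinetics and on an assumed share of reduced samples. A reader might take the largest tabulated figure, -34.0%, as typical. It requires 30% of samples at a visit to come from participants reduced twice from 100, 200 or 400 mg, and nothing in the documents suggests that rate. Nor do the documents support saying that Ctrough is biased low throughout, since the bias is zero where nobody is reduced.

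The matter merits correction because Ctrough in combination is a named secondary endpoint and the remedy is cheap.

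**What to change.** In Section 7.4.2, state that classification by original arm applies to safety and efficacy analyses. In Table 10.3.3-1 and the SAP, add for BMS-986242 Ctrough:

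1. Each sample is linked to the dose actually taken before it.
2. The primary summary by dose and day uses samples taken while on the assigned dose.
3. Samples after a reduction, an interruption or a re-escalation are flagged and listed by actual dose. They are not pooled into the lower dose's primary summary.
4. A dose-normalised summary of all samples is given as a sensitivity analysis.

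The work is a few sentences and a merge of dosing records with the concentration data. It changes no clinical conduct.

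There are two costs. Fewer samples per dose remain at late visits. Some selection also remains, because those reduced may be the high-exposure participants: in the simulation with log SD 0.23, the on-dose mean stays at about 0.91 to 0.96 of its true value, and with log SD 0.5 it falls to 0.81 to 0.92. The on-dose and dose-normalised summaries should therefore be shown side by side, with the number of flagged samples at each visit.

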Cohort tolerability assessment and subsequent dose recommendation may occur when 2 DLT-evaluable participants within a cohort have completed the 6-week DLT observation period (see [Section 7.4.1](#) for criteria for DLTs). DLTs occurring within the 2-week lead-in period (DLT observation period for monotherapy) will be used to fit the BLRM model for monotherapy. DLTs occurring within the 4 weeks of combination period (DLT observation period for combination) will be used to fit the BLRM-copula model. If a potential DLT occurring in any third evaluable participant does not influence the dose recommendation by BLRM (-copula), then the BLRM (-copula)-recommended next dose level may proceed without waiting for the third participant to complete the corresponding DLT observation period after discussion and agreement by the sponsor and investigators. The lower recommended dose from both models will be considered for the next dose escalation. Participants receiving $\geq 75\%$ (11 out of 14 doses) of BMS-986242 in the 2-week lead-in cycle will be considered as DLT-evaluable participants for BMS-986242 monotherapy. Participants who receive at least 1 dose of nivolumab and have been followed at least 5 days and receive $\geq 75\%$ BMS-986242 (21 out of 28 doses) in the 4-week DLT observation period for combination therapy will be considered as DLT-evaluable participants. Continuous re-assessment of dose recommendation by BLRM will be carried out at each dose level after each cohort of participants with consideration of all available DLT information. In order to allow additional safety, PK, and pharmacodynamic assessment, in Part 1 up to 12 additional participants may be enrolled at any dose level at or below the MTD, up to a total of 24 additional participants.

No intra-participant dose escalation is allowed, although dose modifications of BMS-986242 may be permitted (see [Table 7.4.2-1](#)).

[figure not shown]
Sentinel Participant: During dose escalation, a staggered dosing (sentinel participant) approach will be used. In the first dose level, the first participant in both lead-in and combination will receive the Cycle 0 Day 1 or Cycle 1 Day 1 dose(s) of study treatment(s) and be observed for 5 days before additional participants in that cohort receive monotherapy or combination study treatment. In subsequent dose levels, a sentinel participant with a 5 day observation period will be used for Cycle 0 Day 1.

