7.4 Dosage Modification

7.4.1 Dose-limiting Toxicity

For the purpose of guiding dose escalation, DLTs will be defined based on the incidence and grade of AEs for which no alternate cause can be identified.

Part 1: Cycle 0 BMS-986242 (monotherapy lead-in) will have a 2-week DLT evaluation period (DLT1). The combination regimen will have 4-week DLT evaluation period (DLT2). Therefore, the total DLT assessment period is 6 weeks. Participants may proceed from Cycle 0 to Cycle 1 at each cohort unless any of the following events is observed: any DLT, Grade 2 or higher immune-related AEs considered related to BMS-986242 (eg, immune-mediated pneumonitis, colitis, hepatitis, nephritis, renal dysfunction) with the exception of immune-mediated hypothyroidism and hyperthyroidism, or Grade 2 AST and ALT elevation that does not resolve to Grade 1 within 1 week. For Grade 2 AST and ALT elevations that resolve to Grade 1 or baseline within 1 week, participants can be rechallenged with BMS-986242 monotherapy for a minimum of 5 days before proceeding to combination with nivolumab provided there is not a recurrence of Grade 2 event.

The total DLT period is 6 weeks, and participants must have received at least 75% of the BMS-986242 doses and 1 dose of nivolumab with observation for a minimum of 21 days following the first combination treatment dose to be considered evaluable for dose escalation decisions. Based on the predicted human half-life of BMS-986242 of 13 hours, this interval is expected to cover the anticipated timeframe for the occurrence of clinically significant immediate and early-onset AEs related to BMS-986242 monotherapy during Cycle 0 and repeat dosing of BMS-986242 in combination with nivolumab in Cycle 1.

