7.4.1.1 Dose-limiting Toxicities

Dose-limiting Toxicities for DLT1 and DLT2 Periods

Nonhematologic DLT:

A. Hepatic, Nonhematologic DLT

Any of the following events will be considered a hepatic DLT:

- Any \geq Grade 3 elevation of AST, ALT, or total bilirubin
- Grade 2 AST or ALT with symptomatic liver inflammation (eg, right upper quadrant tenderness, jaundice, pruritus)
- AST or ALT $> 3 \times$ ULN and concurrent total bilirubin $> 2 \times$ ULN without initial findings of cholestasis (elevated serum alkaline phosphatase; eg, findings consistent with Hy's law or Food and Drug Administration definition of potential drug-induced liver injury [DILI])*

*Note that this special category of DLT uses ULN rather than Common Toxicity Criteria Grade for definition.

B. Nonhepatic, Nonhematologic DLT

Any of the following events will be considered a nonhepatic, nonhematologic DLT:

- Grade 2 or greater episcleritis, uveitis, or iritis
- Any other Grade 2 eye pain or blurred vision that does not respond to topical therapy and does not improve to Grade 1 severity within 2 weeks OR requires systemic treatment
- Any Grade 3 or greater nondermatologic, nonhepatic, nonhematologic toxicity will be considered a DLT with the following specific EXCEPTIONS:
 - Grade 3 or Grade 4 electrolyte abnormalities that are not complicated by associated clinical adverse experiences, last less than 48 hours, and either resolve spontaneously or respond to conventional medical intervention
 - Grade 3 nausea, vomiting, or diarrhea that lasts less than 48 hours and either resolves spontaneously or responds to conventional medical intervention
 - Isolated Grade 3 elevation of amylase or lipase not associated with clinical or radiographic evidence of pancreatitis
 - Isolated Grade 3 fever not associated with hemodynamic compromise (eg, hypotension, clinical or laboratory evidence of impaired end-organ perfusion)
 - Grade 3 endocrinopathy that is well controlled by hormone replacement
 - Grade 3 tumor flare (defined as pain, irritation, or rash that localizes to site of known or suspected tumor)
 - Grade 3 fatigue
 - Grade 3 infusion reaction that returns to Grade 1 in less than 6 hours

C. Dermatologic DLT

- Grade 3 rash if no improvement (ie, resolution to \leq Grade 1) after a 1- to 2-week infusion delay. Participants who have not experienced a Grade 3 study treatment-related skin AE may resume treatment in the presence of Grade 2 skin toxicity.

- Grade 4 rash of any duration.

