D. Hematologic DLT

- Grade 4 neutropenia \geq 5 days in duration
- Grade 4 thrombocytopenia or Grade 3 thrombocytopenia with bleeding or any requirement for platelet transfusion
- Grade \geq 3 febrile neutropenia for 48 hours
- Grade \geq 3 hemolysis (ie, requiring transfusion or medical intervention such as steroids)
- Grade 4 anemia not explained by underlying disease
-

• In addition to the above criteria, any toxicity that results in a participant not receiving at least 75% of the doses of BMS-986242 and the dose of nivolumab during the DLT evaluation period or causing greater than 2 weeks of dose delay will be classified as a DLT.

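### From the 50 mg cohort up, the DLT-evaluability rules do not require doses at the assigned level, so a dose-reduced participant can enter the model as DLT-free at a dose hardly taken (lead-in) or never taken (combination) in that window

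*Combined protocol and SAP*

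**What the plan says.** **Evaluability is a dose count.** Section 5.1.2.1 sets the lead-in rule ("11 out of 14 doses) of BMS-986242 in the 2-week lead-in cycle will be considered as DLT-evaluable participants for BMS-986242 monotherapy") and the combination rule ("21 out of 28 doses) in the 4-week DLT observation period for combination therapy will be considered as DLT-evaluable participants"). Section 7.4.1 restates it: "participants must have received at least 75% of the BMS-986242 doses and 1 dose of nivolumab". None of the three names a dose level.

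**Reductions are foreseen inside the window.** Table 7.4.2-1 covers any other related event of Grade 3 or higher that does not force discontinuation. Its combination column reads "Decrease 1 level of BMS-986242 (no lower than 25 mg) in combination with same dose of nivolumab"; the monotherapy column gives the same one-level step and the same floor.

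**Some Grade 3 events are not DLTs.** Section 7.4.1.1 exempts, among others, fatigue, isolated amylase or lipase elevation, and "Grade 3 nausea, vomiting, or diarrhea that lasts less than 48 hours and either resolves spontaneously or responds to conventional medical intervention".

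**Classification.** Under Section 7.4.2, a DLT that follows a reduction is charged to the highest dose given. For everyone, including a reduced participant with no DLT, the rule is "For data collection and analysis purposes, all participants will continue to be classified by the original treatment arm".

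**Limits on missed doses and restart.** Section 7.4.1.1 also makes a DLT of "any toxicity that results in a participant not receiving at least 75% of the doses of BMS-986242 and the dose of nivolumab". Section 7.4.2 says "Re-initiation of study treatment cannot occur until AE decreases to" Grade 1 or lower, or baseline. Sections 7.4.3 and 7.4.4 tie restart to the next treatment visit or scheduled time point.

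**The concern.** The dose-toxicity model needs to know whether a participant tolerated a stated dose over a stated window. A count that ignores level, combined with classification by original arm, can give it a DLT-free record at a dose that the participant did not take for most or all of the window. The participant was reduced because of related toxicity, so the record flatters the higher dose and pushes towards escalation.

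The trigger is plausible. Section 3.3.1 reports vomiting and diarrhea in dogs, where the top dose exceeded the MTD, and short Grade 3 vomiting or diarrhea is one of the exempted events. The 25% and 35% overdose limits in Appendix 7, Section 3 are the main statistical protection in the escalation, and they are only as good as these inputs.

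**Working it through.** **1. The plan's own figures.** 0.75 × 14 = 10.5, rounded up to 11; 0.75 × 28 = 21. Both match Section 5.1.2.1. With the Appendix 7 prior means, logit(p) = log(0.3/0.7) + log(d/600) gives 1.8, 3.4, 6.7, 12.5, 22.2 and 30.0% at 25 to 600 mg. Table 4 (By Prior) shows 2, 4, 7, 13, 22 and 30%.

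**2. Combination window, 200 mg cohort.**
- Related Grade 3 vomiting on lead-in Day 13, controlled within 48 hours: not a DLT.
- Days 13 and 14 are held, so 12 of 14 doses are taken, all at 200 mg. The lead-in record is sound.
- Section 7.4.1 bars Cycle 1 for a DLT, certain immune-related events and certain AST/ALT elevations. None applies.
- Cycle 1 starts one level down and 28 of 28 doses are taken at 100 mg.
- Result: evaluable, classified at 200 mg, with 0 of 28 combination doses at 200 mg.

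**3. Lead-in window.** At most 14 − 11 = 3 doses can be lost to toxicity; a fourth triggers the catch-all DLT.
- Restart only at the Day 8 visit: 4 full + 3 held + 7 reduced gives 11 taken, 4 of 11 (36%) at the assigned level. Stopping after Day 1, 2 or 3 leaves 8, 9 or 10 doses, which is a DLT.
- Restart allowed between visits: 1 full + 3 held + 10 reduced gives 11 taken, 1 of 11 (9%) at the assigned level.

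Cohorts at 12.5 and 25 mg are unaffected, because no reduction goes below 25 mg.

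**4. Effect on the lead-in model.** Inputs from Appendix 7: log α₁ ~ N(−0.847, SD 1.53), log β₁ ~ N(0, SD 1), correlation 0, reference 600 mg. The recommended dose has the highest P(0.16 ≤ p < 0.33) among doses with P(p ≥ 0.33) < 25%, at most one level up. Assumption: 0/4 DLTs at every lower level. The posterior was computed on a grid.

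*Kept v excluded, no replacement.* In a first cohort of 4, x/4 and x/3 give the same recommendation for x = 0 to 3 at 50, 100, 200 and 400 mg. At the planned sizes of 4, 7 and 10 with up to 3 DLTs, two patterns change:

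| Cohort | Kept | Excluded | P(overdose) one level up | Recommendation |
|---|---|---|---|---|
| 100 mg | 2/7 | 2/6 | 23.8% v 27.2% at 200 mg | 200 v 100 mg |
| 50 mg | 3/10 | 3/9 | 24.1% v 27.8% at 100 mg | 100 v 50 mg |

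*Kept v replaced, first cohort of 4.* The other three and the replacement each have a DLT with the Table 4 By Prior probability p. Then P(lower) = Σₓ Bin(x; 3, p) × p, summed over those x for which (x+1)/4 gives a lower recommendation than x/4.

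| Dose | p | Contributing terms | P(lower) |
|---|---|---|---|
| 50 mg | 4% | x=1: 3×0.04×0.96²×0.04 = 0.44%; x=2: 0.02% | 0.5% |
| 100 mg | 7% | x=1: 3×0.07×0.93²×0.07 = 1.27%; x=2: 0.10% | 1.4% |
| 200 mg | 13% | x=0: 0.87³×0.13 = 8.56%; x=2: 0.57% | 9.1% |
| 400 mg | 22% | x=0: 0.78³×0.22 = 10.44%; x=1: 3×0.22×0.78²×0.22 = 8.83% | 19.3% |

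For example, 0/4 v 1/4 at 200 mg gives 6.7% v 27.5% overdose probability at 400 mg; at 400 mg it gives 14.5% v 37.3% at 600 mg. A DLT-free replacement restores the same count and changes nothing.

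**5. Combination model.** Appendix 7, Section 2.2.3 gives γ₁ a gamma prior with mean 1.1, 40% probability below 1, and 97.5th percentile log(3) = 1.10. Mean 1.1 with 40% below 1 requires a shape of about 13.5, whose 97.5th percentile is 1.76. The three statements cannot all hold, so no combination figure is offered.

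**The case against.** **Replacement is optional.** Section 7.2 says non-evaluable participants may be replaced, and Section 5.1.2.1 seeks at least 3 evaluable per level, which a cohort of 4 less one still has. Exclusion alone then changes no lead-in recommendation. This stands. A reader might take 19.3% as the chance of a wrong escalation at 400 mg. It is not: it presupposes a reduced participant, an enrolled replacement and 0/4 at every lower level. Under the By Prior rates, 0/4 at each of 25, 50, 100 and 200 mg has probability (0.98 × 0.96 × 0.93 × 0.87)⁴ = 33.6%. Section 5.1.2.1 also takes the lower of the two models' recommendations.

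**Restart may have to wait for a visit.** On the stricter reading of Sections 7.4.3 and 7.4.4, the lead-in extreme is 4 of 11, not 1 of 11. This stands for the lead-in. The combination example is untouched, since it restarts at the Cycle 1 Day 1 visit.

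**Appendix 7 refers to data from administered doses.** That could mean coding by the dose taken. The phrase is generic, while Section 7.4.2 addresses reduced participants directly. The choice matters: moving the participant in the 100 mg, 2/7 case down to 50 mg gives 25.7% at 200 mg, so the recommendation stays at 100 mg.

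**Existing safeguards.** The catch-all DLT responds to doses not received, and reduced doses are received. Table 7.4.2-1 is described as general guidance, and clinicians review all data before each dose decision. They would see the reduction, but the model input would remain wrong.

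**Conclusion.** The point holds as a gap in the evaluability rules and should be fixed. On the text, a DLT-free participant can be counted at an assigned level of 50 mg or above after taking none of the combination doses there. In the lead-in, the participant can be counted after taking only 4 of 11 there, or 1 of 11 if restart between visits is allowed. That no level is required is inferred from silence in Sections 5.1.2.1 and 7.4.1, together with the explicit classification rule in Section 7.4.2.

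The effect is small and runs towards escalation. The lead-in sizes rest on 0/4 at every lower level and, for the replacement figures, on the By Prior rates. A reader might infer that the combination model is materially biased, or that a stated share of cohorts would be mis-escalated. The documents support neither: the γ₁ prior is internally inconsistent, and no rate of such reductions is given. Nor does the point show a fault in the model itself.

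**What to change.** In Sections 5.1.2.1 and 7.4.1, state that for a participant without a DLT the 75% of BMS-986242 doses (11 of 14 in lead-in, 21 of 28 in combination) must be taken at the assigned level in that window. Otherwise the participant is non-evaluable at that level for that window and may be replaced under Section 7.2.

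Also state that:
- participants with a DLT stay counted as Section 7.4.2 now provides;
- the 75% in the catch-all DLT of Section 7.4.1.1 keeps its present meaning, doses at any level;
- every reduction is still reported and weighed in the clinical dose decision.

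The cost is one phrase in two sections, a few clarifying sentences and a few more replacements at 50 mg and above. The exclusion is informative, because these participants leave the model on account of related toxicity; that is why they must stay in the clinical review. The rule also leans cautious: a reduced participant with a DLT is counted, while one without may be replaced.
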